PROTOCOL TITLE: Using factorial design to examine efficacies of technology-based augmentations for improving treatment adherence and skills utilization in a self-help CBT program for binge eating.

Protocol Version Date: April 19, 2022

10. Are prisoners

We will tell subjects verbally at the end of the Phone Screen if they are found to be ineligible for the study. If the subject asks, we will tell them the specific exclusion criteria that made them ineligible for the study.

6) Study-Wide Number of Subjects

We will be enrolling 76 research participants.

7) Study-Wide Recruitment Methods

Does Not Apply

8) Study Timelines

The research received receipt of application from the NIMH in 1st September 2022. The current study will use the first 7-months (September 2022-April 2023) of the study for synchronous development of technology-based intervention systems including Advanced DDS and JITAIs along with self-help CBT program for binge eating. We also conservatively allow 25 months (May 2023-July 2025) of active recruitment time; recruitment rates in our previous seven NIH-funded clinical trials for BN, BED, and/or obesity suggest we can reach our target of 76 research participants within this time period. Treatment will consist of 12 weeks of the self-help CBT program delivered via smartphone app for binge eating over a period of approximately 4 months.

9) Study Endpoints

The expected outcomes from the curret study will include the following:

- 1) The Advanced DDS with coaches will independently produce greater improvements in treatment adherence and skills utilization.
- 2) JITAIs system will independently produce greater improvements in treatment adherence and skills utilization.
- 3) Advanced DDS with coaches and JITAIs systems as adjuncts to self-help CBT program for binge eating will be feasible and acceptable. Specifically for feasibility of Advanced DDS with coaches and JITAIs, there will be a high number of patients screened per month, high % of eligible patients enrolled, low treatment attrition, high study retention, high treatment adherence, high treatment fidelity. Specifically for acceptability of Advanced DDS with

PROTOCOL TITLE: Using factorial design to examine efficacies of technology-based augmentations for improving treatment adherence and skills utilization in a self-help CBT program for binge eating.

Protocol Version Date: April 19, 2022

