coaches and JITAIs, there will be high adherence and competency ratings from the feedback questionnaires of 20% of the sessions for each group treatment.

4) The Advanced DDS with Coaches and JITAIs will produce greater improvements in binge eating frequency at post-treatment, and 3 months follow-up.

5) Improvements in treatment adherence and skills utilization will be associated with reductions in binge eating.

10) Procedures or Methods Involved

Aims and Design. The primary aims of the study will be to (1) Test target engagement, i.e., that each factor including Advanced DDS with Coaches and JITAIs produces greater improvements in treatment adherence and skills utilization, (2) Test the feasibility and acceptability of two intervention factors as adjuncts to self-help CBT program for binge eating; (3) Test the initial efficacy, i.e., that each factor including Advanced DDS with Coaches and JITAIs will produce greater improvements in binge eating frequency at post-treatment, and 3 months follow-up; and (4) Test target validation, i.e., that improvements in treatment adherence and skills utilization will be associated with reductions in binge eating. Exploratory aim will be to quantify the intervention factors interaction effects, which may be partially additive (because intervention factors overlap and/or there is diminishing return), fully additive, or synergistic (in that intervention factor may partially depend on each other). This study is being conducted to test a novel approach to deliver evidence-based treatment in a routine clinical setting. The proposed study will use a factorial (2 x 2) design to evaluate the independent and interactive efficacy of two intervention factors (Advanced DDS with Coaches and JITAIs) when added to a self-help CBT program at improving treatment adherence, skills utilization and clinical outcomes. The self-help CBT program will be delivered through the smartphone application. Both intervention factors have two levels, either ON or OFF (Assignment is not dynamic, i.e., the ON versus OFF assignment at baseline remains as such for the entirety of the program) producing 4 possible treatment combinations.

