Randomization. Participants will be randomized into one of the 4 treatment conditions and will receive 12 weeks of treatment. Of note, the treatment conditions being offered in the current study are superior than standard of care for binge spectrum eating disorders. The standard of care for binge spectrum eating disorder and bulimia nervosa is behavioral treatment. In this project, all the participants will receive self-help CBT program, which is an evidence based-treatment program for binge spectrum eating disorders and is superior to standard of care. As such, there is no potential of randomizing subjects into a condition that is less than standard of care for their eating disorders.

Treatment Conditions.

Base self-help program. All participants will receive 12 weeks of the self-help CBT program delivered via a self-help smartphone application (app). Participants will access the self-help application that will guide them through the treatment and goals setting. Participants will also use the base self-help app during the week to self-monitor all eating and ED

PROTOCOL TITLE: Using factorial design to examine efficacies of technology-based augmentations for improving treatment adherence and skills utilization in a self-help CBT program for binge eating.

Protocol Version Date: April 19, 2022

behaviors. Below we describe the program detail and how the treatment will be deployed via this program.

Self-help CBT app. The self-help CBT program will be delivered through the smartphone application. The application will deliver treatment via 12 learning modules that will be based on Chris Fairburn's "Overcoming Binge Eating" self-help book, the most widely used self-help resource for binge eating, that has shown to produce moderate-to-large effect size reductions in binge eating. Treatment modules will aim to 1) provide psychoeducation on maintenance factors for binge eating, 2) teach CBT skills designed to interrupt these maintenance factors, and 3) coach participant to set personalized goals each week. Modules will be completed in succession over the course of 12-weeks and a new module will be made open each week. Consistent with standard self-help CBT for binge eating, the app will allow for electronic self-monitoring (or, tracking) of eating and eating disorder behaviors. A list of the data to be collected via self-monitoring forms can found in the *Data collected through self-help app document*.

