Addition of intervention factors to self-help CBT program to accomplish factorial design. As mentioned above, participants will be randomized to one of the 4 treatment combinations. The standard of care for binge spectrum eating disorder and bulimia nervosa is behavioral treatment. In this project, all the participants will receive self-help CBT program based on [name] evidence-based treatment program for binge spectrum eating disorders, and is superior to standard of care. As such, there is no potential of randomizing subjects into a condition that is less than standard of care for their eating disorders. Below, we describe the treatment when each of the two intervention factors are turned ON and OFF and when synergies occur between both intervention factors, as applicable.

Advanced Digital Data Sharing with Coaches When Advanced DDS with Coaches is turned ON, coaches having a bachelor's degree in health-related fields (e.g., psychology, nursing, nutrition etc.) will have access to a secure web portal called the digital data portal. Our team has successfully developed and used a digital data portal for ED treatments in a recent CBT+ clinical trial (R34MH11602). This portal will accomplish four key functions including, 1) gather data on target behaviors from the base self-help app (i.e., uptake of weekly module, self-monitoring compliance and skills utilization), 2) synthesize participants' behavioral data on treatment targets, 3) flag data to increase salience of behaviors needing improvement and 4) use sophisticated algorithms to generate recommendations for intervening on the identified data patterns. Using the information from the digital data portal, the coaches will send weekly emails to facilitate improvement in treatment targets. Coaches will send one email a week for a total of 12 emails over the course of treatment.

When Advanced DDS with Coaches is turned OFF, participants' will not have their data shared and will not receive emails from the coaches.

Just-in-time, adaptive interventions (JITAI) The proposed JITAI system will use machine learning algorithms to intervene on 1) treatment adherence, and 2) skills utilization during the 12 weeks of treatment. When JITAI are turned ON, the base self-help app will be used to deliver targeted, personalized and automated interventions during machine learning

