Blood Draws. As is standard, blood testing to assess for medical complications associated with purging is conducted based on severity of purging behavior. If participants demonstrate purging 3 or more times per week and are deemed unsafe to continue study participation by their PCP, they will be removed from the study to receive medical care of worsened purging behavior, and thus, will not undergo anymore blood testing for the study assessments. If the severity of purging is low (i.e., less than 3

PROTOCOL TITLE: Using factorial design to examine efficacies of technology-based augmentations for improving treatment adherence and skills utilization in a self-help CBT program for binge eating.

Protocol Version Date: April 19, 2022

episodes per week), participants may undergo blood testing once during the study for medical monitoring and to receive PCP clearance to continue study participation in addition to study assessments.

Feasibility and Acceptability. Assessment of feasibility will include number of patients screened per month, % of eligible patients enrolled, treatment attrition (% of patients that prematurely terminate treatment), study retention (% of patients that complete all study assessments), treatment adherence, treatment fidelity. Acceptability will be assessed using the Feedback Questionnaire. During treatment each session will be audio-recorded and 20% of the sessions for each group treatment will be randomly selected for adherence and competency ratings by a blinded IE.

Outcome Measures

Rater-Administered Measures:

- ***Eating Disorder Examination (EDE)***. The EDE is a widely utilized, semi-structured interview for the assessment of eating disorder symptoms. The EDE interview will be audio recorded and will be used to confirm research participant's eligibility. The EDE has been updated to the newest version of this measure.
- ***Mini International Neuropsychiatric Interview (MINI)***. The MINI is a structured psychiatric diagnostic interview.
- ***Body Mass Index (BMI)***. For BMI, height (via stadiometer) and weight (via medical-grade, digital scale) will be assessed in the clinic prior to treatment onset and at each assessment point. This data will be used to calculate BMI. In the case of remote assessments, research participants will weigh themselves at home using digital scales and take their heights using yard sticks or measuring tape.

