- ***Eating Disorder Diagnosis***. This measure will be used to determine a research participant's eating disorder diagnosis based on the presence, frequency, and duration of pathological behavioral symptoms a research participant endorses at the assessment point.
- ***Feedback Questionnaire***. This measure will be used to assess research participant's overall enjoyment and perceptions of the treatment and assessments. The measure

PROTOCOL TITLE: Using factorial design to examine efficacies of technology-based augmentations for improving treatment adherence and skills utilization in a self-help CBT program for binge eating.

Protocol Version Date: April 19, 2022

will be conducted as an interview at mid-treatment (after 6 weeks of treatment) and post-treatment (after 12 weeks of treatment).

Self Report Measures

- ***Demographics Questionnaire (DQ)***. The Demographics Questionnaire will assess information such as age, sex, gender, sexual orientation, ethnicity, and SES.
- ***Dieting and Weight History Questionnaire (DWHQ)***. The DWHQ evaluates weight suppression, weight history, current and previous dieting history.
- ***Beck Depression Inventory-II (BDI-II)***. The BDI-II measures depression symptomatology over the past 2 weeks.
- ***Quality of Life Inventory (QOLI)***. The Quality-of-Life Questionnaire assesses quality of life across several life domains
- ***Short Positive and Negative Affect Scale (PANAS)***. The PANAS assesses positive and negative affect over a specified period of time.

Other measures

- ***Treatment adherence*** will be indicated by number of completed modules within 12 weeks of treatment, number of pages visited, number of worksheets completed, and goals setting each week using the app and self-monitoring compliance (i.e., number of days when self-monitoring was completed).

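### Adherence and competency ratings are to come from 20% of audio-recorded treatment sessions, but no condition has a treatment session to record

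*Protocol*

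**What the plan says.** Protocol section 10, Feasibility and Acceptability, ends with a rating rule for the treatment period: "each session will be audio-recorded and 20% of the sessions for each group treatment will be randomly selected". The ratings are for adherence and competency, and a blinded independent evaluator makes them. Just before this, the same paragraph closes its list of feasibility measures and turns to acceptability: "treatment adherence, treatment fidelity. Acceptability will be assessed using the Feedback Questionnaire".

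Protocol section 9, item 3, also names fidelity among the expected feasibility results: "low treatment attrition, high study retention, high treatment adherence, high treatment fidelity". It then describes the acceptability result as "high adherence and competency ratings from the feedback questionnaires of 20% of the sessions for each group treatment".

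On how treatment is delivered, section 10 describes a 12-module self-help app for everyone. For the coaching factor it says: "Coaches will send one email a week for a total of 12 emails over the course of treatment". JITAI messages are automated and appear in the app. When both factors are ON, coaches may also write messages and schedule them through the data portal.

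The Outcome Measures list says of the Feedback Questionnaire: "This measure will be used to assess research participant's overall enjoyment and perceptions of the treatment and assessments".

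The SAP text for Primary Aim 2 sets criteria for recruitment, retention and satisfaction. It does not mention fidelity.

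**The concern.** The rating rule assumes live treatment sessions that can be recorded and sampled, and the intervention described has none. Section 9 then takes the same 20% ratings from a participant questionnaire about enjoyment and perceptions, which cannot show whether a coach followed the intended procedure or did so competently. The two sections disagree on the source of the ratings and on the endpoint they serve, and neither source can supply them.

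At stake is treatment fidelity, which the protocol lists twice as a feasibility measure without giving it a unit, a threshold or any other data source. Participant adherence (modules, pages, worksheets, goals, self-monitoring days) is defined separately and measures something else. It records what participants do, not whether coaches acted on the portal's recommendations or whether JITAI messages went out when triggered. In a pilot meant to inform a larger trial, a planned measure of delivery is worth having, and delivery data not captured during treatment may be hard to recover.

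**Working it through.** The plan has no computed figure to reproduce. The only number in the rule is the 20% sampling fraction, which is a design choice. The check sets the rule beside what each condition receives (Protocol section 10, Treatment Conditions and the paragraphs on the two factors).

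| Condition | What is delivered | Treatment sessions to record |
|---|---|---|
| DDS OFF, JITAI OFF | App | 0 |
| DDS ON, JITAI OFF | App, 12 weekly coach emails | 0 |
| DDS OFF, JITAI ON | App, automated in-app messages | 0 |
| DDS ON, JITAI ON | App, 12 weekly coach emails, automated messages, extra coach-written messages | 0 |

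Ratings available under the rule = 0.20 × 0 = 0 in every condition.

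Other places where a session might be found:

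- **Audio recordings.** Those that section 10 (Assessment Procedure, EDE) and section 22 provide for are of assessment interviews, and they serve assessor reliability.
- **Weekly group meetings.** In the section 10 text on intervention quality, these are meetings of the coaches with their supervisor. Participants do not attend. The same text says that coaches give their support by email.
- **Therapists, study visits and a clinical intake.** Section 10 (Screening) and section 5 mention these in passing, but neither describes a treatment session.
- **Group treatment.** This may mean group sessions or simply each trial arm. The count is zero either way.

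The size of a workable replacement, using coach emails as the rated unit, is as follows:

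- Enrolment is 76 (Protocol section 6). The allocation ratio is not stated, so equal allocation is assumed: 76 / 2 = 38 participants with DDS ON.
- At 12 emails each, with no dropout: 38 × 12 = 456 emails.
- A 20% sample: 0.20 × 456 = 91.2, about 91 emails.
- As a lower illustration, suppose that the 15% attrition allowed for in the SAP power section all fell before the first email: 0.85 × 456 = 387.6 emails, and 0.20 × 387.6 = 77.5, about 78.

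For attrition up to that allowance the workload is therefore roughly 78 to 91 emails. The extra coach-written messages in the both-ON condition are not counted, because their number is not given. The two DDS-OFF conditions contribute none.

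**The case against.** The strongest reply is that this is a misplaced sentence with little consequence. Several parts of that reply stand.

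- **The link to fidelity is inferred.** The protocol never says that the session ratings are the fidelity measure, and section 9 files them under acceptability. They are only the sole candidate offered.
- **Acceptability is not lost.** A reader of section 9 alone might think that the impossible ratings are its only measure. Section 10 assigns acceptability to the Feedback Questionnaire and schedules it at mid- and post-treatment, and the SAP adds Likert satisfaction and coded interview ratings.
- **No planned Aim 2 analysis fails.** A reader might infer that Primary Aim 2 loses a component. Its SAP criteria are recruitment, retention and satisfaction, and all three can still be assessed.
- **A null result would not be uninterpretable.** A reader might infer that the trial could not tell an ineffective factor from an undelivered one. Coach emails are written and fixed in number, the coaches' work is reviewed weekly, JITAI messages are automated, and app use is recorded. What is missing is a planned fidelity rating, not all evidence of delivery.

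The reply does not remove the core of the point. The rule as written cannot be carried out, the two protocol sections contradict each other, and a listed endpoint is left without a usable measure.

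There is also a caution about the remedy. Coach emails exist only when DDS is ON, so whoever rates them learns that assignment. Independent evaluators conduct the outcome assessments, and section 10 already describes assessors as both unblinded and blind. Giving the email ratings to an evaluator who also assesses outcomes would add a blinding problem.

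**Conclusion.** The point holds in a limited form. The adherence and competency ratings cannot be made as specified: zero are obtainable in all four conditions, and this rests on the documents' own description of delivery. Sections 9 and 10 of the protocol also conflict on where the ratings come from and what they measure. Treatment fidelity is therefore a listed feasibility endpoint with no workable definition, on the inference that these ratings were meant to supply it.

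The damage is confined to that endpoint. The figure of about 91 emails out of 456 describes the scale of the replacement, not of the defect. It assumes equal allocation and no dropout. The correction should be made, and it is most useful while delivery data can still be captured.

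**What to change.** 1. In Protocol section 10, replace the session-recording sentence with a random 20% sample of coach emails in the two DDS-ON conditions, rated for adherence to the portal's recommendation and for competency.
2. Have existing trained staff who do not conduct outcome assessments make these ratings. Drop the description of the rater as blinded, since the emails reveal DDS assignment. State whether coach-written messages in the both-ON condition are also sampled.
3. Report JITAI fidelity as the share of triggered messages that were delivered. The documents do not say that triggering and delivery are logged, so confirm this first. Confirm also that the portal keeps the recommendation each email was based on.
4. Correct section 9, item 3, so that acceptability comes from the Feedback Questionnaire, as section 10 already says.
5. In the SAP text for Primary Aim 2, either add fidelity as a descriptive measure or remove it from the protocol's endpoints, so that the documents agree.

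The cost is protocol and SAP wording, time to rate roughly 78 to 91 emails, and a check of what the app and portal log. If JITAI delivery turns out not to be logged, adding that would be extra work that the documents do not allow to be sized.

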Assessments will be conducted by unblinded assessors at baseline, mid-treatment, post-treatment, and at 3-month follow-ups. Assessments will be for a total of 3 hours in length. Assessors for the baseline, mid-treatment, post-treatment, and 3 month follow up will be research coordinators employed and paid by the WELL Center and Ph.D students at Drexel University. Three hours of the assessment is a semi-structured interview in which the participants will be using a zoom link via Drexel's HIPAA compliant Zoom platform the assessor sent prior to the interview to meet with the assessor who conducts the interview with the participant. Total length of participation in this study will be about 7 months from the baseline assessment to the 3-month follow-up assessment. As the study continues, the status of the trial will be updated on <http://www.ClinicalTrials.gov> as different phases of the study start and end (including but not limited to “not yet recruiting”, “recruiting”, “active not recruiting”, and “completed”).

This study will have 2 kinds of blind assessors. One type of blind assessor is the study coordinator. The study coordinator is a full-time paid employee on the study. As part of their job responsibilities, they will conduct assessments for this current study. The other type of assessors is graduate students. Students serve as assessors on clinical trials being conducted in a research lab to receive specialized training and supervision in conducting clinical interviews for assessing eating disorders. Typically, graduate students are obligated to fulfill 8 hours of training time in the specialized research lab without getting paid. Graduate students will be asked to conduct assessments within these 8 hours of free lab time and hence, will not be paid for conducting the assessments. In the conditions with Advanced DDS with Coaches, coaches will be unblinded throughout the 12-week program. Coaches will know the study condition and diagnosis of the specific patients they've been assigned in order to facilitate improvement in treatment targets of the patients they've been assigned. Coaches will be blinded to the clinical outcomes from treatment for the patients they are assigned to. They will be blinded to all clinical outcomes data collected at different assessment time points.

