Some research participants undergoing treatment may become uncomfortable or anxious. Research participants will be asked to abstain from binge eating and purging, a process that is difficult given the nature of the illness. Research participants will also be asked to provide information regarding a number of significant health behaviors during the assessments. However, all assessment instruments have been used in past research without incidence and research participants will be informed that they can skip questions or discontinue participation at any time. Although we expect most research participants to show a reduction in disordered eating symptoms, it is possible that some research participants could experience a worsening of eating disorder symptoms during the study period. If a worsening of symptoms is identified, we will follow the protocol described below to ensure the safety of research participants. This protocol is based on those used in our team's current NIH funded trials for BN and BED. If a coach identifies worsening binge eating symptoms or compensatory behaviors, the principal investigator and research coordinator will be notified. If the increases in disordered eating symptoms are determined to be transient, mild, and unlikely to result in adverse health consequences, efforts will be made to keep the research participant enrolled in the current study and treatment condition consistent suggestions will be made to address current symptoms. If the increases in eating disorder symptoms are sustained, clinically significant, or likely to cause health consequences, we will consult with the research participant's PCP to discuss whether medical management is needed. Research participants with frequent and intense eating disorder pathology will be medically monitored by their PCP throughout the trial and will only be allowed to participate if it is deemed medically appropriate by their PCP. Research participants will be informed that research personnel will inform the PCP if there is a change in symptom status such as an increase in restrictive eating behavior or increase in purging behavior that may require additional medical management. It is expected that these research participants will have regular appointments with their PCP, the frequency of which will be determined by the treating physician. In order to facilitate care, consent will be obtained prior to treatment onset for two-way communication between study staff and the treating physician. As part of the trial, treating physicians will also be provided current practice guidelines as set forth by the American Academy of Psychiatry regarding eating disorders. Research participants without a PCP, with limited access to their PCP, or with a PCP that is unable to effectively monitor their eating disorder symptoms, will be assisted in locating a PCP that better fits their needs. We will not be

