Department of Psychology. The Department of Psychology is actively engaged in research initiatives to advance the science and practice of psychology. The faculty is highly collaborative, frequently cooperating on research projects, co-mentoring doctoral students, and providing consultation to one another as needed. Faculty and students collaborate on a great deal of

PROTOCOL TITLE: Using factorial design to examine efficacies of technology-based augmentations for improving treatment adherence and skills utilization in a self-help CBT program for binge eating.

Protocol Version Date: April 19, 2022

research; a total of 110 conference presentations and 61 publications (including four books) resulted from these efforts during the past few years. Extramural funding totaling over \$10 million (including the full number of ongoing awards) support this work in 2011. The department currently houses several prominent research laboratories that focus on research similar to the proposed study, including acceptance-based behavioral treatment and eating pathology.

Laboratory Space. Because this study will occur remotely, no laboratory space will be required.

Computing Facilities. At present, all personnel have desktop and laptop computers with broadband Internet connections and necessary word processing and statistical software. The system is protected by firewalls and password protection for security of sensitive data.

Independent Evaluator Training, Supervision, and Integrity. Outcome assessments will be conducted by independent evaluators (IE). IEs will be highly trained and closely supervised clinical psychology doctoral students. IEs will be trained until they reach 100% agreement on eating disorder diagnosis and acceptable reliability ($> .80$) on EDE scoring. Assessments will be audio-recorded for review. The identity of participants will not be discussed to prevent the possibility of this information influencing feedback and rating decisions. If reliability falls $< .80$, retaining procedures will be implemented. If this is insufficient, the IE will be replaced. Twenty randomly assigned selected tapes will be reviewed to compute reliability statistics for diagnoses and ratings.

23) Prior Approvals

Does not apply.

24) Recruitment Methods

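### The protocol calls outcome assessors both blind and unblinded; if they are to be blind, the Feedback interview and the coach alert can reveal condition before the EDEs used for Aim 3

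*Protocol*

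**What the plan says.** **Blinding.** Protocol section 10, Assessment Procedure, states: "Assessments will be conducted by unblinded assessors at baseline, mid-treatment, post-treatment, and at 3-month follow-ups". The next paragraph describes two kinds of blind assessor, the study coordinator and graduate students: "One type of blind assessor is the study coordinator".

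**Who rates.** The same section says: "Assessors for the baseline, mid-treatment, post-treatment, and 3 month follow up will be research coordinators employed and paid by the WELL Center", together with PhD students. Section 22, on independent evaluators, says: "IEs will be highly trained and closely supervised clinical psychology doctoral students", and names no coordinator.

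**Feedback interview.** Section 10 lists the Feedback Questionnaire among the rater-administered measures, next to the EDE. On its content: "This measure will be used to assess research participant's overall enjoyment and perceptions of the treatment and assessments". It "will be conducted as an interview at mid-treatment (after 6 weeks of treatment", and again at post-treatment. It is the stated acceptability measure: "Acceptability will be assessed using the Feedback Questionnaire". The Assessment Schedule marks it at the same mid- and post-treatment time points as the EDE.

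**Coach alert.** Under section 15, when a coach sees binge eating or compensatory behaviour getting worse, "the principal investigator and research coordinator will be notified".

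**Use of the ratings.** SAP Primary Aim 3 models change in binge eating frequency and EDE global score. It adds contrasts for both factors at post-treatment and 3-month follow-up.

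**The concern.** Participants see the coach emails and the in-app prompts, so they cannot be masked. The rater is the only person in the outcome assessment who can be. The EDE is a semi-structured interview that involves rater judgement, so knowledge of condition can affect the score.

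The contradiction over blinding is a defect in itself. Settling it in favour of blind raters would not be enough, because two stated procedures would still carry information about condition to people who may rate the EDE. The second also tells the rater about the participant's clinical course and can occur only where a coach is involved, so it is not balanced across the levels of the DDS factor.

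**Working it through.** The documents give no figure on this point, so the check sets the passages side by side.

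1. **Is there a blind?** Section 10 gives both answers. If the unblinded statement governs, there is nothing to break and the ratings are openly unmasked. The remaining steps assume that blind raters are intended.

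2. **Route 1, Feedback interview.** It is rater-administered, is held as an interview, concerns the treatment, and falls at the same visits as the EDE. Section 10 describes the assessment as a Zoom interview with one assessor, so one person doing both is the natural reading. Questions about the treatment invite mention of emails or prompts, or of their absence. No text assigns the interview to someone else, puts it after the EDE, or asks participants not to disclose.

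3. **Route 2, coach alert.** With DDS OFF, section 10 says that data are not shared and no coach emails are sent. A coach report therefore implies DDS ON. It goes to the research coordinator. Section 10 lists research coordinators as assessors and calls the study coordinator a blind assessor.

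4. **Safeguards.** Randomization by the statistician (section 10) protects allocation, not later masking. Not discussing participants' identity (section 22) does not conceal condition. Reliability above .80 and review of twenty tapes check agreement between raters, not masking. Section 10 keeps clinical outcomes from coaches but does not stop information passing from coach to rater.

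5. **Timing.** The mid-treatment Feedback interview precedes the post-treatment and 3-month EDEs. A coach alert during the 12 weeks does too.

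6. **What a rating shift would do (illustration only; the shift is assumed).** I used the linear-change power formula for the time-by-factor test: noncentrality = N × d² × rel / 4, with rel = 1 / (1 + 12/(M(M² − 1))) for a variance ratio of 1, and F(1, N − 2). With M = 4, rel = 1/(1 + 12/60) = 0.833.
   - Plan's own figure: N = 64 and d = 0.78 give 64 × 0.6084 × 0.833 / 4 = 8.11 and power of 80.1%, so the SAP's 64 is reproduced. Then 64/0.85 = 75.3, rounded up to 76.
   - Replace d by an assumed average rating shift between factor levels, with no true effect and N = 76:

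| Assumed shift (standardized) | Noncentrality | False-positive rate |
|---|---|---|
| 0 | 0 | 5% |
| 0.1 | 0.158 | 6.8% |
| 0.2 | 0.633 | 12.3% |
| 0.3 | 1.425 | 21.8% |

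The shift is the average over everyone in a factor level. If only some DDS-ON participants trigger an alert, route 2 contributes only that fraction of its per-participant effect. The documents give neither the fraction nor the effect, nor the direction of any bias.

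**The case against.** The strongest reply is that the point is conditional. If assessors are unblinded, no blind is lost, and the real defect is the contradiction in section 10. That is right, which is why the contradiction comes first here. Correcting that one word would still leave both routes open.

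Second, the documents do not say who conducts the Feedback interview, in what order the measures run, or whether one rater follows a participant throughout. The mid-treatment EDE may come before the interview at that visit. This stands: the procedures can reveal condition, and the text does not show that they will.

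Third, if section 22 governs and only doctoral students rate, a coach alert need not reach an EDE rater. The protocol also does not state that section 15's research coordinator is section 10's study coordinator. This weakens route 2 and leaves route 1 untouched.

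Fourth, an alert shows one factor of the 2 × 2 and only for participants reported as worsening. This stands.

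Fifth, the SAP does not name the source of binge eating frequency. That it comes from the EDE is a reasonable inference. The SAP also says it will rely on effect sizes and confidence intervals for EDE global. A rating bias would distort an estimate as readily as a test.

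**Conclusion.** The point holds as a conditional one. The statements on whether assessors are blind, and on whether the coordinator rates outcomes, conflict and must be reconciled. If raters are to be blind, the Feedback interview and the coach alert can disclose condition before the EDEs behind the Aim 3 contrasts, and no stated safeguard prevents it. The second route is confined to DDS-ON arms and discloses DDS status and clinical course, not JITAI status.

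A reader might infer that raters following the plan will know the condition at post-treatment and follow-up. On that reading, 76 × 2 = 152 of 76 × 3 = 228 post-randomization EDEs (67%) would be exposed, or all 228 if the Feedback interview always came first. The documents do not support this. Those counts need full attendance, the same rater for the Feedback interview and every later EDE, and disclosure by every participant. None of these is stated, and the SAP itself allows 15% attrition. The frequency of unmasking and the size of any bias are unknown; the shifts in the table are assumptions.

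**What to change.** 1. Reconcile sections 10 and 22: state whether EDE raters are blind, and whether coordinators rate outcomes.
2. If they are blind, complete and lock the EDE before the Feedback interview at each visit.
3. Have the Feedback interview done by an existing staff member who does not rate that participant's later EDEs. The Likert satisfaction items in SAP Primary Aim 2 can be collected by self-report in REDCap, which the trial already uses, so that only the coded interview needs a person.
4. At the start of each EDE, ask participants not to mention coach emails or app prompts.
5. Leave the section 15 safety notification unchanged. Once a coordinator has received a coach alert, have another existing blind assessor rate that participant's later EDEs.
6. Record any suspected unblinding, so that its extent can be reported.

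The cost is a few lines of protocol text and slightly less scheduling flexibility among the existing coordinator and graduate-student assessors. At full attendance there are 76 × 2 = 152 Feedback interviews to assign in this way. This is a matter of rostering and does not in itself call for new staff.
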